TITLE: INFLUENZA VACCINATION IN PLASMA CELL DYSCRASIAS

Coordinating Center: Winship Cancer Institute of Emory University

Winship PI: [name] MD MPH

Laboratory investigator: [name] MBBS

Sanofi: Fluzone HD

Commercial Agent: Prevnar 13 (PCV 13)

Statistician: [name] Winship BBISR

Protocol / Date:

Initial / 7-May-2019
V 1.1 / 22-May-2019
V 1.2 / 13-Jul-2019
V 1.3 / 31-Oct-2019
V 1.31 / 13-Nov-2019
V 2.0 / 9-Mar-2020
V 2.1 / 7-Apr-2020
V 2.2 / 3-Jul-2020
V 2.3 / 20-Jul-2020
V 2.4 / 14-Sep-2020

CTCAE version: 5.0

[figure not shown]
Total consented patients: 175 total
50 patients (2019-2020) of which 23 were evaluable
125 patients (2020-2021)

Text color legend

Blue text
Blue text

Instructions and detailed for correlative science for laboratory #1
Instructions and detailed for correlative science for laboratory #2

SCHEMA

This is a phase IV randomized trial of 148 evaluable patients with a plasma cell disorder to be enrolled as early as possible in the influenza season through 15-Dec.

Fluzone HD refers to TIV formulation for 2019-2020 influenza season and QIV formulation for 2020-2021 season.

After eligibility is confirmed, patients will be randomized 1:1 to either an experimental arm where each patient receives three injections of Fluzone HD and a control arm where each patient receives one injection of Fluzone HD.

All patients receive Prevnar at week 5 if they have not received either PCV13 or PPSV23 in that calendar year.

STANDARD OF CARE AND RESEARCH INTERVENTIONS

Timing	Week 1	Week 5	Week 9	Week 17	Week 21
Standard of care tests	
 Blood tests Clinic visit 	Prevnar (PCV13)			Myeloma proteins
Research	
 Consent Eligibility Research blood Fluzone HD #1 	Research blood	Fluzone HD #2	Fluzone HD #3	Research blood

Timing	Week 1	Week 5	Week 9	Week 17	Week 21
Standard of care tests	
 Blood tests Clinic visit 	Prevnar (PCV13)			Myeloma proteins
Research	
 Consent Eligibility Research blood Fluzone HD #1 	Research blood			Research blood

Table of Contents

1. PRIMARY HYPOTHESES, OBJECTIVES, AND ENDPOINTS	6
2. EXPLORATORY SCIENTIFIC HYPOTHESES, OBJECTIVES, AND ENDPOINTS	6
3. BACKGROUND	6
3.1 INFLUENZA OVERVIEW	6
3.2 INFLUENZA RISK IN ADULT CANCER PATIENTS	6
3.3 INFLUENZA VACCINATION RESEARCH IN ALLOGENEIC TRANSPLANT PATIENTS.....	7
3.4 MULTIPLE MYELOMA.....	7
3.5 MYELOMA PATIENTS AND INFLUENZA.....	8

1. PRIMARY HYPOTHESES, OBJECTIVES, AND ENDPOINTS

Clinical		
Hypothesis	Objective	Endpoint
Continuous FluZone HD throughout the flu season will improve hemagglutination inhibition (HAI > 40) as measured at the end of the season compared to those patients that receive FluZone HD once.	Demonstrate an absolute 25% increase in seroprotection, defined as HAI>40 against all strains, at week 21 in the experimental arm compared to the control arm.	HAI will be measured in all patients at baseline, week 5, and week 21 to calculate seroconversion at week 5 and seroprotection at week 21. Seroconversion: Pre-vaccination HAI<10 and a post-vaccination HAI>40 or a pre-vaccination HAI >10 and a \geq 4-fold rise in post-vaccination HAI at week 5.

The above measurables will appear in the results section of www.clinicaltrials.gov at trial completion

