3.2 Influenza risk in adult cancer patients

There is no perfect sign of acquired immunosuppression in humans. Neutropenia is often the consequence of chemotherapy that is watched most closely as it is associated with lethal bacterial infections especially when the absolute neutrophil count is less than 500/uL, and not surprisingly is associated with more influenza-

related complications than in the general population¹. In two studies of different cancer patient populations, absolute lymphocyte count of less than 200/uL was an independent predictor of progression to influenza-related pneumonia².

A review of vaccine immunogenicity among patients with both liquid and solid tumors demonstrated decreased seroconversion rate among cancer patients receiving chemotherapy (17% to 52%) compared to cancer patients not receiving chemotherapy (50% to 83%) and compared to healthy controls (67% to 100%)³.

People undergoing chemotherapy or those that have acquired profound immunosuppression seen after allogeneic stem cell transplantation are at increased risk of influenza-related complications^{4,5}. People at highest risk include those with impaired cell-mediated and antibody-mediated immunity, as reflected by a decrease in the number or function of T and B cells⁶. Influenza-related hospitalization rates are four times higher and mortality 10 times higher among people with cancer compared with the general population^{7,8}.

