3.6 Assessment of influenza vaccination response

Influenza vaccines work by activating antigen-specific B-cells to proliferate and differentiate into plasmablasts that secrete protective antibodies and memory B cells that can rapidly proliferate and differentiate into plasmablasts upon re-encountering the immunizing antigen. Studies in healthy individuals demonstrated a transient plasmablast response after vaccination peaking at around 7 days after vaccination at which point it makes up to 16% of all B-cell, and returning to baseline levels by day 14. Memory B-cell response, on the other hand, peaks at 14-28 days after vaccination followed by a slower rate of decline²⁹⁻³¹. A subset of the plasmablasts migrate to the bone marrow and become long-lived plasma cells secreting antigen-specific antibodies for protracted periods of time. Memory B-cell and plasma cells provide a remarkably stable immunological memory that can persist over 50 years after vaccination in humans. Interestingly, plasma cells are not intrinsically long-lived and only a finite number of plasma cells survive after an immune response irrespective of the number of plasma cells generated, suggesting that plasma cells require a specialized niche for survival³². It remains unclear what factors direct the differentiation of activated, antigen-specific B-cells into either memory B-cells or plasmablasts and plasma cells. Studies in mice suggested that the B-cell repertoire in the memory B-cell and the plasma cells compartments differ in terms of antigen-binding affinity and breadth³³.

Generation of immunological memory is the hallmark of adaptive immune responses. Clinically, this can be measured by determining seroprotection, defined as the percentage of subjects with a post-vaccination hemagglutination antibody inhibition (HAI) titer $> 1:40$; and seroconversion, the percentage of subjects with either a pre-vaccination HAI titer $< 1:10$ and a post-vaccination HAI titer $> 1:40$ or a pre-vaccination HAI titer $> 1:10$ and a minimum four-fold rise in post-vaccination HAI antibody titer by week 5.

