Clearance of viral infection and vaccine responses are dependent on cell mediated immunity. The most common serologic measurement of antibody protection following influenza vaccine administration is an HAI titer of 40 or higher. However, this cutoff corresponds to an estimated 50% clinical benefit of preventing influenza infections, based on studies in young healthy adults^{34,35}. It is believed that cell-mediated immunity declines with age, which may help explain why the elderly are more vulnerable to influenza infections. HAI titers have also been shown to be lower in the elderly compared to young adults. Based on studies showing increased serologic protection, Fluzone HD (TIV) was FDA approved in 2009 for adults aged 65 and older, the QIV formulation in Nov-2019.

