6.5 Schedule of events

Experimental arm

Assessment	Screening + First visit	Week 5 ^a	Week 9 ^a	Week 17 ^a	Week 21 ^a
Signed informed consent	X				
Vital signs	X				
CBC/d/p ^d	X				
CRP, Serum IG's, LDH	X				
Myeloma proteins ^e	X				X
Blood for research ^f	40 mL	40 mL			40 mL
Fluzone HD	X		X	X	
Prevnar (PCV13)		X			
Record grade \geq 2 adverse events ^g	X		X	X	
Influenza-like illness update ^b		X	X	X	X
PFS and OS ^h					X

Control arm

Assessment	Screening + First Visit	Week 5 ^a	Week 9 ^a	Week 17 ^a	Week 21 ^a
Signed informed consent	X				
Vital signs	X				
CBC/d/p ^d	X				
CRP, Serum IG's, LDH	X				
Myeloma proteins ^e	X				X
Blood for research ^f	40 mL	40 mL			40 mL
Fluzone HD	X				
Prevnar (PCV13)		X			
Record grade \geq 2 adverse events ^g	X				
Influenza-like illness update ^b		X	X	X	X
PFS and OS ^h					X

- a. Assessments on these days can be performed within a \pm 5 day window. Subsequent visits (weeks 5, 9, 17, 21) are based on the actual time of Fluzone HD vaccination, not the pneumonia vaccination.
- b. Involves contact between study personnel and the patient regarding influenza-like illness and SAEs. An in-person visit is not required.
- c. All patients (N=148) will have research blood drawn for correlative science. In both arms, blood will be obtained at baseline, week 5, and week 21. The first 20 patients in each group (n=40 total), split evenly between intervention arm (20 experimental, 20 control), had additional blood drawn 1 week after each Fluzone HD dose (week 2 for control arm and weeks 2, 10, and 18 in the experimental arm) – this was completed 17-Nov-2019.
- d. CBC, differential, and platelets will be performed pre-vaccination.
- e. If not done with results available within 30 days of initial vaccination, a modified myeloma disease assessment requested but not required to include SPEP and free light chains if either were measurable per IMWG criteria in the past. Serum IgD or IgE are requested if a monoclonal IgD or IgE were present in the past. For patients with an IgA monoclonal protein, Hevylite IgA can be used to replace serum immunoglobulins and SPEP.
- f. Peripheral blood samples will be obtained and analyzed as described in correlative science section.

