8.1.3 Specimen analysis

HAI titer will be assessed.

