10.4.5 Analysis of influenza response and disease status endpoints

HAI will first be measured and summarized with mean and standard deviation at different time-points, respectively. Paired t-test will be further used to test whether there is significant change in HAI at different time points from baseline, respectively. Two sample t-test will be used to compare the change in HAI from baseline between two groups, at different time-point, respectively. Chi-Square test will be used to compare the Seroconversion and Seroprotection between two groups, respectively. Logistic regression model will be used to compare adjusted difference in Seroconversion and Seroprotection between two groups after adjusting for other factors, respectively.

Spearman/Pearson correlation coefficient will be used to measure the relationship between correlation between HAI, predefined risk of influenza-like illness (low, moderate, high), respectively. Finally Mixed model will be employed to test their correlations over the whole period with and without

adjusting for other factors, respectively. Kaplan Meir method, Log-rank test, and Cox model will be used to test the relationship between peak HAI and PFS.

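### The seroconversion rule covers baseline HAI below 10 and above 10 but not exactly 10, so a patient starting at 10 is scored a non-responder whatever the rise (minor)

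*Combined protocol and SAP*

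**What the plan says.** Section 1 (primary hypotheses, objectives and endpoints) defines seroconversion at week 5 by "Pre-vaccination HAI<10 and a post-vaccination HAI>40 or a pre-vaccination HAI >10", the last condition being joined to a rise of at least four-fold. Section 3.6 gives the definition again, with the second branch worded "or a pre-vaccination HAI titer $> 1:10$ and a minimum four-fold rise in post-vaccination HAI antibody titer by week 5". Its first branch likewise needs a baseline below 1:10.

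No other section fills in the value between the branches. Section 8.1.3 says only "HAI titer will be assessed"; it gives no dilution series, lower limit or coding rule. Section 10.4.5 uses seroconversion without redefining it.

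The endpoint is used in two ways. Section 1 closes with "The above measurables will appear in the results section of www.clinicaltrials.gov at trial completion", and Section 10.4.5 states "Chi-Square test will be used to compare the Seroconversion and Seroprotection between two groups, respectively", followed by a logistic regression with adjustment. On timing, footnote c of Section 6.5 says "In both arms, blood will be obtained at baseline, week 5, and week 21", and the schedule in that section puts the second Fluzone HD dose at week 9, in the experimental arm only.

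**The concern.** A responder definition should place every possible baseline in exactly one branch. Here one value is left out, and it lies at the boundary that separates the branches. On a two-fold scale starting at 10 it would be the lowest reportable titre, and so possibly a common one in a population described as responding poorly to vaccination.

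At stake is the week 5 seroconversion rate. An analyst who follows the text must record clear responders as failures. An analyst who uses the sensible rule departs from the protocol, and if that happens after results are seen by arm, the departure can be challenged as data-driven.

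**Working it through.** **1. The rule applied to single results.** Assumed titres are two-fold (<10, 10, 20, 40, 80, ...). The last column changes only the second branch, from >10 to ≥10.

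| Baseline | Post-vaccination | Rise | As written | With ≥10 |
|---|---|---|---|---|
| <10 | 80 | – | yes | yes |
| 10 | 20 | 2-fold | no | no |
| 10 | 40 | 4-fold | no | yes |
| 10 | 80 | 8-fold | no | yes |
| 10 | 320 | 32-fold | no | yes |
| 20 | 80 | 4-fold | yes | yes |

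For a post-vaccination titre of 80, baselines of <10 and 20 both count, but the 8-fold rise from 10 between them does not. No immunological reading explains that pattern; it comes from the signs alone.

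**2. What does not depend on the rule.** The sample size in Section 10.3 uses only the HAI >40 rates: p1 = 0.333, p2 = 0.585, alpha 0.05, power 80%, equal arms (B = 0.5), R² = 0.1. With P = (0.333 + 0.585)/2 = 0.459:

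n = [1.960·√(P(1−P)/B) + 0.842·√(p1(1−p1) + p2(1−p2)(1−B)/B)]² / [(p1−p2)²(1−B)]

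= [1.960·√0.4966 + 0.842·√0.4649]² / [0.0635 × 0.5] = 120.4

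Dividing by 1 − 0.1 gives 133.8, so 134 as stated. No seroconversion rate enters.

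**3. Illustrative size of the loss, one strain.** None of these inputs is in the documents; all are assumptions.
- Baseline log2 titre is normal, with geometric mean (GM) 5 to 80 and SD 1.5 or 2.
- The log2 rise is normal, with mean 1, 1.5 or 2 and SD 1.5.
- Titres are floored to two-fold steps from 10, with <10 as one class.

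Loss = P(reported baseline = 10 and reported post-vaccination titre ≥ 40)
= ∫ f(b)·P(b + rise ≥ log2 40) db, over b from log2 10 to log2 20.

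| Baseline GM | Loss, percentage points |
|---|---|
| 5 | 5.5–9.9 |
| 10 | 7.1–15.4 |
| 20 | 7.2–15.7 |
| 40 | 5.7–10.4 |
| 80 | 2.7–5.9 |

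The minimum is 2.7 (GM 80, SD 1.5, mean rise 1) and the maximum 15.7 (GM 20, SD 1.5, mean rise 2). Between about 7% and 25% of baselines are exactly 10.

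Worked example (GM 20, SD 2, mean rise 1.5): the rate is 26.3% as written and 35.9% with ≥10, a loss of 35.9 − 26.3 = 9.6 points.

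The loss is the same whether the post-vaccination cut-off is >40 or ≥40, because a baseline of 10 would be judged only on the four-fold rise.

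**The case against.** The best case for leaving this alone is that little depends on it. The hypothesis and objective in Section 1, and the hypothesis in Section 10.1, concern week 21 seroprotection. Seroconversion appears only in the endpoint column. At week 5 the arms have had identical influenza vaccination, so the comparison in Section 10.4.5 has no treatment contrast to distort. The titres are kept and can be reclassified at any time. All of this stands, and it is why the point is minor.

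The loss figures are also open to challenge. They rest wholly on assumed distributions, and the top of the range needs a mean four-fold rise. Section 3.6 defines seroconversion as a percentage of subjects, and the documents do not say whether it is judged per strain or across strains, so a per-strain loss is not the loss in the reported rate. This too stands; the range is an illustration and not a bound.

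A lost sign in the PDF is not a convincing explanation. The same sentence in Section 1 keeps its ≥ for the fold rise, and Section 3.6 repeats the strict signs independently.

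A reader might go further and infer that the seroprotection cut-off is wrong too. Section 3.6 also says "The most common serologic measurement of antibody protection following influenza vaccine administration is an HAI titer of 40 or higher", Section 3.5 reports earlier myeloma trials at ≥40, and that section gives the 58% and 33% of the preceding randomized trial without a cut-off. The documents do not support that inference. This trial's rule is >40 in Sections 1, 3.6, 10.1 and 10.3, which is a permissible choice, and the planning rates are labelled as HAI >40 rates. Nothing shows that they were measured otherwise, so no loss of power can be claimed.

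**Conclusion.** The gap is certain on the text: a baseline of exactly 10 cannot seroconvert under either statement of the rule. Its effect is to lower the week 5 seroconversion rate. The amount is not in the documents. It is about 3 to 16 percentage points per strain under the assumptions shown, and zero if the assay never reports 10, in which case the correction is harmless.

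A reader might infer that the gap biases the comparison of arms or weakens the trial's main result. Neither is shown. Both arms have had one dose by week 5, and neither the 134 observations nor the week 21 seroprotection comparison uses this definition. Severity: minor.

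**What to change.** In Sections 1 and 3.6, change the second branch of the seroconversion definition to a pre-vaccination HAI ≥10 with a ≥4-fold rise. Leave the first branch and the >40 cut-off as they are. Make the change before HAI results are seen by arm, so that it cannot be read as a response to the data.

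The cost is one sign in two places and a short amendment, which Section 13.2 requires the IRB to approve. No new samples, assays or patients are needed, and the sample size stays as it is.

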2. EXPLORATORY SCIENTIFIC HYPOTHESES, OBJECTIVES, AND ENDPOINTS

Measurement of B & T-cell subsets and flu-specific responses as a way of understanding immunosuppression in this patient population, correlating with influenza-like illness.

3. BACKGROUND

3.1 Influenza overview

Influenza is an acute viral respiratory illness from three main types (A, B, and C), where type A is subcategorized based on viral surface glycoproteins hemagglutinin (HA) and neuraminidase (NA). Primary influenza pneumonia is a rare but severe, complicated by otitis media and exacerbations of chronic respiratory conditions. Other complications include otitis media, exacerbations of chronic respiratory disease, myocarditis – often the concern is for influenza infection to ‘set the stage’ for a subsequent lethal bacterial pneumonia. Those at high-risk for complications include those with cardiopulmonary diseases, chronic care facility residents, and those over 65 years old.

Influenza vaccines contain antigens of the circulating influenza viruses and are intended to trigger antibody-mediated protection. Influenza A viruses undergo continual changes in the hemagglutinin (HA) and neuraminidase (NA) proteins, which necessitate annual updates. Current influenza vaccines are available as inactivated vaccine (IV), trivalent (TIV) or quadrivalent (QIV), usually A/H1N1, A/H3N2, and either one or two strains of B), and as a recombinant vaccine which may be TIV or QIV.

3.2 Influenza risk in adult cancer patients

There is no perfect sign of acquired immunosuppression in humans. Neutropenia is often the consequence of chemotherapy that is watched most closely as it is associated with lethal bacterial infections especially when the absolute neutrophil count is less than 500/uL, and not surprisingly is associated with more influenza-

related complications than in the general population¹. In two studies of different cancer patient populations, absolute lymphocyte count of less than 200/uL was an independent predictor of progression to influenza-related pneumonia².

A review of vaccine immunogenicity among patients with both liquid and solid tumors demonstrated decreased seroconversion rate among cancer patients receiving chemotherapy (17% to 52%) compared to cancer patients not receiving chemotherapy (50% to 83%) and compared to healthy controls (67% to 100%)³.

People undergoing chemotherapy or those that have acquired profound immunosuppression seen after allogeneic stem cell transplantation are at increased risk of influenza-related complications^{4,5}. People at highest risk include those with impaired cell-mediated and antibody-mediated immunity, as reflected by a decrease in the number or function of T and B cells⁶. Influenza-related hospitalization rates are four times higher and mortality 10 times higher among people with cancer compared with the general population^{7,8}.

3.3 Influenza vaccination research in allogeneic transplant patients

An open-label randomized trial included 78 patients at least a week before a planned allogeneic stem cell transplant⁹. Odds ratio for all-cause mortality was 1.05 (95% CI 0.4 to 2.77) among those vaccinated. Influenza-related mortality was similar as well between the groups (2/40 among vaccinated versus 2/38 among non-vaccinated). Documented influenza infection rate was similar in vaccinated and unvaccinated patients (3/40 versus 4/38, respectively). GMTs at 30 days post-vaccination among the vaccinated population were significantly higher for influenza A/H1N1 and influenza A/H3N2 strains (15 versus 10, p=0.03 and 30 versus 12.5, p< 0.001, respectively).

Another open-label randomized trial enrolled 73 adults after allogeneic HSCT, of which 35 were randomized to receive an adjuvanted influenza vaccine (Fluad) and the rest (38) randomized to a non-adjuvanted influenza vaccine (Influvac)¹⁰. There were five cases (14%) of laboratory-confirmed influenza among patients receiving the adjuvanted vaccine compared to three cases (8%) in the non-adjuvanted vaccine group. Vaccine immunogenicity, reported as seroconversion rate, seroprotection rate, and GMTs, was not significantly higher in the adjuvanted vaccine group. This study was underpowered for conclusions regarding seroprotection or to identify differences in influenza-like illness between the groups.

3.4 Multiple myeloma

Multiple myeloma (MM) affects approximately 83,000 US citizens and over 50% of patients die within 5 years of diagnosis; more than half of patients older than 70 years with low albumin and high β 2microglobulin die within a year of diagnosis^{11,12}. Of the 30,330 new cases estimated in 2016 in the U.S.¹³, MM is twice as common in African Americans as Caucasians, and genetic changes accumulate as plasma cells degenerate from monoclonal gammopathy of undetermined significance, through smoldering myeloma, to MM¹⁴. MM is characterized by fractures, anemia, kidney failure, and hypercalcemia with a

predisposition for bacterial infections from the inherent immunoparesis and varicella reactivation often aided by proteasome inhibition¹⁵.

Advances in high-dose chemotherapy and stem cell transplantation have improved overall survival and event-free disease periods in patients with MM, but relapses are inevitable^{16,17}. New therapeutic agents, such as new generation proteasome inhibitors (carfilzomib and ixazomib), immunomodulatory agents (lenalidomide and pomalidomide, the histone deacetylase inhibitor (HDACi) panobinostat, and monoclonal antibodies (elutuzumab and daratumumab) have shown promising clinical benefit in patients with relapsed or refractory disease. Current treatments include regimens using proteasome inhibitors and/or immunomodulatory agents in combination with HDACi, alkylating agents, and monoclonal antibodies.

